In this 3-arm randomized controlled trial (RCT), parent-child dyads will be assigned to a 10-week group-based intervention, delivered to parents, targeting adolescent substance use prevention and diet improvement through parenting and family-focused strategies. The proposed study will be conducted in partnership with our longtime research collaborator, the ADA. ADA has a demonstrated record of successfully recruiting and retaining thousands of Mexican heritage and other Latino parents into *Realizing the American Dream* (RAD), their academic success program with no substance use prevention or nutrition content. ADA's trained community facilitators will lead the parents' groups (15 parents per group) via three conditions: substance use prevention and healthy nutrition (FPNG+; n=498 parent-child dyads); substance use prevention only (FPNG; n=498 parent-child dyads), or a comparison condition (RAD; n=498 parent-child dyads). The three curricula will be delivered through ADA programming, offered to families of 6th – 8th grade students (11-14 years old) in 18 different schools (6 per condition). Randomization will occur at the school level, each school randomly assigned to one of the three conditions. Participants will be consented for the specific condition their school is randomized to (i.e. the consenting materials will only describe the condition the school is assigned to).

Participant recruitment

We will recruit parent-child dyads consisting of one parent and one youth enrolled in 6th, 7th or 8th grade. Following inclusiveness policies from our community partner, the American Dream Academy (ADA), parents of children enrolled in other grades will also be included if interested in the program, but their children will not be part of the study. Inclusion criteria are as follows:

Youth:

- ages 11-14
- enrolled in 6th-8th grade at the time of recruitment from the ADA programs

Adults:

- age 18 or older
- parent/caregiver/guardian of an eligible youth or parent of a child enrolled in participating schools who expresses interest in the program

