Power calculations considered design effects related to the clustering of outcome means by school sites. The total estimated sample size is 1494 parent-child dyads, across 18 schools. Based on data from the FPNG effectiveness trial, the level of clustering is low for our outcomes, including an intraclass correlation equal to 0.01, a student level R-square of 0.25, and a school level R-square of 0.03.² Because the effect size for substance use outcomes ($d=0.20$; FPNG vs. C) is lower than the expected effect size for nutrition outcomes ($d=0.78$; prior non-related intervention study), the total sample size is calculated for substance use outcomes. Accounting for these parameters, the power of this design is 0.802. For the subsample, the estimated sample size is 126 households across 18 schools – 7 per school. The average effect size of .69 is calculated based upon prior work on home food availability of vegetables, fruits, and desserts. Given the above stated parameters, the power of this design is 0.814.

All analyses will be conducted using multilevel analyses in Mplus,²⁷ with families clustered within schools. This analysis accounts for the clustering which, if uncorrected, may result in biased standard errors.²⁸ All analyses will employ a robust maximum likelihood estimator to adjust for any non-normality in the distributions of outcomes and to best control for Type I errors.²⁹ The analyses will also utilize full-information maximum likelihood (FIML)³⁰ to conduct intent-to-treat analyses that account and adjust for attrition and any item missing data.

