We will use both baseline adjusted general linear model procedures (i.e., variants of multiple regression) and latent change modeling to test intervention efficacy. In all models, because the FPNG Plus is the intervention condition of interest, all analyses will use FPNG Plus as the reference group. The two remaining conditions (FPNG and Comparison) will be compared with the reference group. The first method will predict short-term (T2) and then long-term (T3) post-test outcome measures (e.g., adolescents substance use and diet outcomes), while controlling simultaneously for the baseline (T1) measure of the particular outcome. Latent-change models³¹ will test whether and how changes over time in the outcomes differ significantly. Latent-change models will enable the assessment of change between T1 and T2 separately from change between T2 and T3. This examination will simultaneously test for improvements manifested during the course of the intervention (i.e., between T1 and T2) and for improvements maintained following the completion of the intervention (i.e., between T2 and T3). For mediation analyses, we will employ multivariate linear regression path analyses.^{32,33} Each mediation model will test the indirect path between the intervention condition at T1 and outcome measures at T3 (e.g., adolescents substance use and nutrition outcomes) mediated through family functioning, parenting strategies, and parents' social support at T2. Mediation models will control for baseline (T1) measures of the particular mediator and outcome. We will employ a bias-corrected bootstrap approach to test the indirect effect.³⁴

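### Does the mediation bootstrap need a stated resampling unit and a small-sample reference with six schools per arm?

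*Combined protocol and SAP*

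**What the plan says.** The Study design section randomises schools, not families: "18 different schools (6 per condition). Randomization will occur at the school level". The Data Analysis Plan gives the size as "The total estimated sample size is 1494 parent-child dyads, across 18 schools", and says of clustering that "the level of clustering is low for our outcomes, including an intraclass correlation equal to 0.01". That ICC is given for outcomes; none is given for the mediators.

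On estimation the plan states "All analyses will be conducted using multilevel analyses in Mplus", with families nested in schools and a robust maximum likelihood estimator. Efficacy has its own models: "We will use both baseline adjusted general linear model procedures (i.e., variants of multiple regression) and latent change modeling to test intervention efficacy".

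Mediation comes after that: "For mediation analyses, we will employ multivariate linear regression path analyses". The target is set by "Each mediation model will test the indirect path between the intervention condition at T1 and outcome measures at T3", with family functioning, parenting and parental social support at T2 as mediators and adjustment for the T1 mediator and outcome. Inference is covered by one sentence: "We will employ a bias-corrected bootstrap approach to test the indirect effect". The plan names no resampling unit, no level for the slope and no small-sample correction.

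**The concern.** Condition is assigned to whole schools, so the condition-to-mediator path is a contrast between two sets of six school means. A bootstrap of six units understates their variance, and its interval has no t-type allowance for so few units. Resampling families alone would be worse, because it ignores the school component altogether. The multilevel sentence shows that clustering is to be respected, but it does not by itself choose among resampling schools, resampling schools and then families, or simulating from the fitted model.

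At stake is the claim about mechanism. The Introduction's central hypothesis is that the programme acts by strengthening communication and family functioning. If the test runs at two to three times its nominal level, a programme that left the mediator unmoved could be reported as working through it.

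**Working it through.** The plan states no error rate for this test, so there is no figure of its own to reproduce.

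**Inputs.** From the documents: 3 arms, 6 schools per arm, 1494/18 = 83 families per school, ICC 0.01 (for outcomes). Assumed: the same ICC for the mediator, no effect of condition on the mediator, a standardised mediator-to-outcome slope b of 0.05 to 0.30, and a two-sided 5% test per contrast.

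**Closed form for the condition-to-mediator path** (this governs the error rate when b is clearly non-zero).

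- *Schools within arm.* The bootstrap variance is (6-1)/6 = 5/6 of the unbiased value. The effective cut-off is 1.96 × √(5/6) = 1.789, and P(|t10| > 1.789) = 10.4%.
- *Maximum likelihood multilevel model, normal reference.* The variance factor is 15/18 = 5/6, and P(|t15| > 1.789) = 9.4%.
- *Schools, then families.* The variance of a school mean is 0.01 + 0.99/83 = 0.01 + 0.0119 = 0.0219. The second stage adds the within-school part, 0.0119, again. Average bootstrap variance relative to truth is 5/6 + 0.0119/0.0219 = 0.83 + 0.54 = 1.38. Integrating over the 10-df variance estimate gives a rejection rate of about 2.9%, before bias correction raises it a little.

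So the two-stage version does not understate the variance at ICC 0.01. It overstates it by more than enough to offset the small number of schools.

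**Simulation of the whole indirect effect**, pooled slope, ICC 0.01, 2,500 trials per cell, no baseline covariates; false positives per contrast:

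| Method | b = 0.05 | b = 0.15 | b = 0.30 |
|---|---|---|---|
| Schools within arm | 9.2% | 12.1% | 11.1% |
| Schools across all 18 | 7.2% | 9.8% | 9.0% |
| Normal draws from the ML model | 6.5% | 11.0% | 9.4% |
| Schools, then families | 1.6% | 4.6% | 3.4% |

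At b = 0 every method is at 2% or less. Runs with baseline covariates (the plan's R-squares, or baselines unrelated to follow-up), at b of 0.15 to 0.30, gave 9.5-13.2% for schools within arm, 7.7-10.7% for schools across all 18, and 2.8-5.9% for two-stage. Taken together, the ranges are about 8-14% for one-stage and 3-6% for two-stage.

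**Between-school slope**, ICC 0.01, b = 0.05 / 0.15 / 0.30: schools within arm 1.3% / 2.2% / 4.8%; two-stage 4.9% / 5.3% / 5.5%. The one-stage inflation is gone.

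**Sensitivity to the mediator ICC.** At b of 0.15 to 0.30 with a pooled slope, two-stage gave about 5-8% at ICC 0.02 and 7-9% at ICC 0.05, five times the documented value.

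**Would a t-based test be better?** The alternative is a Monte Carlo interval with the condition-to-mediator path on 18 - 3 = 15 df. Its level depends on the standard error used. With the maximum likelihood standard error the closed form is P(|t15| > 2.131 × √(5/6) = 1.945) = 7.1%. In simulation of that path at ICC 0.01 the rates were 5.0% with an unbiased school-mean standard error, 6.3% with maximum likelihood and 8.1% with a cluster-robust one. For a true 0.20 SD effect on the mediator, power for the indirect effect at b = 0.15 / 0.30 was 61.6% / 59.9%, against 62.3% / 54.7% for the two-stage bootstrap. If a between-school slope is meant, the t-based version has only 4-9% power.

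**The case for a change.** The strongest case for a change is that several readings fit the multilevel commitment, that their error rates run from about 3% to 14%, and that nothing stops the choice being made after the data are seen. The test is used repeatedly: three mediators, several outcomes and two contrasts against FPNG+. The mechanism is part of the central hypothesis. One clause would settle the unit and needs no new data.

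Much of this stands. The omission is plain, the one-stage rates reproduce in closed form and in simulation, and even the two-stage version drifts above 5% if a mediator clusters much more strongly than the outcomes.

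What does not follow is that the plan is in error. Inflation requires a one-stage scheme, a pooled slope and a moderate b together, and the documents commit to none of the three. The slope links parent-side mediators at T2 to youth outcomes at T3 after adjustment for both baselines, so a weak slope cannot be excluded. The worst reading, families alone (about 13-23% at ICC 0.01), conflicts with the plan's own statement on clustering. Replacing the bootstrap would fix a debatable choice of slope, and under the robust maximum likelihood estimation already planned it could itself run at about 6-8%.

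**Conclusion.** No change is needed. The plan leaves open a detail of a secondary mechanism analysis. An analyst who follows its multilevel commitment can resample schools and then families, at about 3-6% false positives per contrast for ICC 0.01 and a pooled slope of 0.15 to 0.30 SD. One-stage school resampling would give about 8-14% under the same assumptions, so the choice is not trivial, but the inflation is absent for a between-school slope and for a slope near zero. The conclusion rests on the mediators clustering about as weakly as the outcomes are said to; near ICC 0.05 the two-stage rate would reach about 7-9%. Efficacy conclusions do not depend on this test. Against the two-stage bootstrap, the t-based alternative shows no power advantage at b = 0.15 and about five points at b = 0.30, and it holds 5% only with an unbiased school-level standard error. That is not enough to prefer it to the planned method.
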